#### **5.4.2 Definition of Baseline Values**

Unless otherwise specified, the baseline value is defined as the value collected at the time closest to, but prior to, the start of study drug administration.

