- a Screening assessments are performed within 28 days before the C1D1 MLN0128 dose. Screening assessments performed no more than 3 days before Screening; Day -1 will qualify as baseline assessments and need not be repeated, unless otherwise specified. Screening; Day -1 is defined as the day before first dose of study drug; screening assessments must be completed by Screening; Day -1.
- b Patients will attend an EOS/Early Termination visit 30 to 40 days after receiving their last dose of MLN0128.
- c Vital sign measurements include blood pressure (diastolic and systolic), heart rate, and temperature.
- d The C1D1 single, 12-lead ECG can be collected 2-4 hours after dosing.
- e When the timing of a PK or safety laboratory blood sample coincides with the timing of ECG measurements, the ECG will be completed before the collection of the blood sample.
- f Baseline CT (with contrast) or MRI scan of the chest, abdomen, and pelvis must be obtained within 4 weeks before the first dose of MLN0128 and at C3D28, after which point CT (with contrast) or MRI may be performed Q3C (ie, C6D28, C9D28, C12D28, etc) as clinically indicated, according to standard of care. The same imaging modality (CT [with contrast] or MRI) should be used throughout the study. Scans are permitted up to 7 days in advance of the study visit. For long term patients, defined as study participation (≥ 1 year, a CT (with contrast)/MRI of chest, abdomen, and pelvis will be obtained at intervals of up to every 4 cycles (plus or minus 7 days) as clinically indicated.
- g Including serious pretreatment events; see Section 9.1.1 for definition.
- h A single dose of 40 mg MLN0128 will be administered on C1D1; patients continuing treatment with MLN0128 after C1D3 at the discretion of the investigator will receive a maximum dose of 30 mg MLN0128 administered on a QW schedule.
- i Patients will be administered an antiemetic agent (0.25 mg palonosetron) as an intravenous infusion over 30 seconds, at least 30 minutes before study drug administration.

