- j A serum β -hCG pregnancy test will be performed only for patients of childbearing potential during screening and again at C1D1 if the screening test was performed more than 4 days before the first dose of any study drug. The results must be negative within 4 days before the first dose of MLN0128 is administered (ie, within the 4 days before C1D1), or as otherwise required by local regulations. Additional pregnancy testing may be performed during the study at the discretion of the investigator, upon request of an independent ethics committee/institutional review board, or if required by local regulations.

Screening ^a	Treatment Cycles											EOS/ Early termina- tion ^b	
	Cycle 1					Cycle 2		Cycle 3		Cycle	Cycle 5 and beyond		
	Day -28 to Day-1	Day 1	Day 2 (24hr postdose)	Day 3 (48hr postdose)	Day 15 (± 2 days)	Day 1	Day 15 (± 2 days)	Day 1	Day 28 (-7 days)	Day 1	Day 1	Day 28 (-7 days)	

- k The hematology and chemistry blood samples for C1D1 may be collected within 4 days before dosing to ensure patient eligibility on study Day 1. If screening clinical laboratory testing was performed within 4 days before the C1D1 dose, it need not be repeated on C1D1. For all other visits, assessments may be performed \leq 24 hours before the study visit. Hematology includes CBC with differential consisting of the following: hemoglobin, hematocrit, leukocytes (WBC), differential WBC count, neutrophils, and platelets. Machine counts are acceptable. The chemistry panel consists of the following: sodium, potassium, carbon dioxide, chloride, blood urea nitrogen, creatinine, bilirubin, alkaline phosphatase, aspartate aminotransferase, alanine aminotransferase, lactate dehydrogenase, gamma glutamyl transferase, albumin, glucose, urate, calcium, phosphate, and magnesium.
- l For screening, creatinine clearance must be \geq 50 mL/min based either on Cockcroft-Gault estimate or based on a 12- or 24-hour urine collection.
- m Fasting glucose will be measured in the clinic. Patients are required to fast overnight (nothing except water and/or medications after midnight or for a minimum of 8 hours before the assessment) for each of these measurements, beginning Cycle 1, Day 4; see [7.4.16](#) for fasting requirements.

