For the Screening; Day -1 and Cycle 1, Day 1 study visits, fasting serum glucose will be measured at the clinical facility. In addition, all patients will be issued a glucometer and trained to use it to monitor their daily predose fasting blood glucose (FBG) levels at home for the days on which glucose is not measured at the clinic. Patients will be instructed to notify the study staff immediately with any abnormal readings (ie, ≥ 150 mg/dL) for further instructions on the management of hyperglycemia. In-home glucose monitoring is not required on days when fasting glucose is measured in the clinic.

To mitigate nausea and vomiting known to occur at a 40 mg dose of MLN0128, patients will be administered an antiemetic agent (0.25 mg palonosetron) on Cycle 1, Day 1.

After collection of the 10-hour postdose PK/ECG assessment on Cycle 1, Day 1, patients will be furloughed from the study site. The Holter recorders will not be removed during this furlough period.

MLN0128**Clinical Study Protocol C31002 Protocol Amendment 2**

On Cycle 1, Day 2 and Cycle 1, Day 3, patients may eat and drink up to approximately 2 hours before arriving at the study site for PK/ECG evaluations.

On Cycle 1, Day 2, patients will report to the clinical facility at least 1 hour before the 24-hour postdose PK/ECG (triplicate) assessments. After the PK/ECG assessments are completed, the Holter recorders will be removed and patients will be furloughed from the study site.

On Cycle 1, Day 3, patients will report to the clinical facility at least 1 hour before the 48-hour postdose assessments, which will represent the final study endpoint-specific planned PK/ECG assessments.

Patients may continue to receive MLN0128 if, in the opinion of the investigator, the patients are deriving clinical benefit, until they experience disease progression. Patients continuing treatment with MLN0128 at the discretion of the investigator will receive a dose of MLN0128 up to 30 mg QW. Dose escalation will not be permitted, and a maximum of 2 dose reductions (for patients experiencing study drug-related toxicity) will be permitted. Patients will return to the study site for follow-up visits at the time points in the [Schedule of Events](#). Treatment may continue until disease progression, unacceptable MLN0128-related toxicity, withdrawal of consent, or for up to 12 months (whichever occurs first).

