7.4.16 Requirements for Fasting Periods

On Screening; Day -1 and Cycle 1, Day 1, patients will be given the option to report to the site fasted or after having a light morning meal, as long as the meal has been completed at least 2 hours before the scheduled baseline triplicate ECG on each day. If patients report to the site fasted, they should do so with adequate time (approximately 3 hours before the scheduled baseline triplicate ECG) in order to eat standard, light breakfast provided by the site that must be completed at least 2 hours before the scheduled baseline triplicate ECG on each day. Patients will be instructed not to eat for the next 6 hours (ie, 2 hours before the 0-hour, predose time point and until completion of the collection of the 4-hour postdose PK/ECG assessments). A standard, light lunch will be provided. Light meals will be administered at the same times on Screening; Day -1 and Cycle 1, Day 1.

On Cycle 1, Day 2 and Cycle 1, Day 3, patients may eat and drink up to approximately 2 hours before arriving at the study site for PK/ECG evaluations; see Section 7.4.19 and Section 7.4.13.2.

Beginning with Cycle 1, Day 4, patients will be instructed to fast overnight (nothing except water and/or medications after midnight or for a minimum of 8 hours) for daily glucose monitoring; see Section 7.4.17 and Section 7.4.18. Starting with Cycle 1, Day 8, patients are advised to take their doses of study drug with a light meal.

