7.4.17 Fasting Glucose

Fasting glucose will be measured at the time points specified in the [Schedule of Events](#) before administration of MLN0128. Patients are required to fast overnight (nothing except water and/or medications after midnight or for a minimum of 8 hours) for each of these measurements beginning on Cycle 1, Day 4; see Section [7.4.16](#).

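### The SAP's last-predose baseline rule has no fasting condition for glucose, so some baselines may be fed while later scheduled fasting-glucose values are fasted

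*SAP*

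**What the plan says.** **Baseline.** SAP 5.4.2: "Unless otherwise specified, the baseline value is defined as the value collected at the time closest to, but prior to, the start of study drug". For glucose, SAP 5.10.2 makes no exception. It lists glucose once, under clinical chemistries. It commits to shift tables of CTCAE grade from baseline to worst post-baseline value and to scatter plots of baseline against worst value. Change from baseline is promised only as an and/or alternative to actual values.

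**Label of the sample.** Protocol 4.1: "For the Screening; Day -1 and Cycle 1, Day 1 study visits, fasting serum glucose will be measured at the clinical facility".

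**Meals on those mornings.** Under protocol 7.4.16 a patient either arrives after a light morning meal or arrives fasted about 3 hours before the baseline ECG, "in order to eat standard, light breakfast provided by the site that must be completed at least 2 hours before" that ECG. Then: "Patients will be instructed not to eat for the next 6 hours (ie, 2 hours before the 0-hour, predose time point". The restriction lasts to the end of the 4-hour assessments.

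**When the glucose fast starts.** Protocol 7.4.17 requires an overnight fast, or at least 8 hours, "for each of these measurements beginning on Cycle 1, Day 4". Schedule of Events note m says the same: "for each of these measurements, beginning Cycle 1, Day 4".

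**Earlier samples.** Note a, which allows for exceptions: "Screening assessments performed no more than 3 days before Screening; Day -1 will qualify as baseline assessments and need not be repeated". Note k: "The hematology and chemistry blood samples for C1D1 may be collected within 4 days before dosing". The note k panel includes glucose and carries no fasting condition.

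**The concern.** The sample is labelled fasting, but both permitted routines for that morning include a meal, and the rule that would make the sample fasting does not apply until three days after the first dose. Later scheduled fasting-glucose samples do require the fast. The SAP then picks the baseline by time alone. A patient can therefore enter the glucose shift table with a fed value before treatment and fasted values after it.

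Hyperglycemia is an effect already seen with this drug (protocol 1.2 and 6.8.2), and safety is a secondary objective. A baseline raised by a meal may hide an upward shift. A reader of the table could not tell fed baselines from fasted ones.

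**Working it through.** The plan gives no figure on this point, so there is none to reproduce. The check sets the passages against each other and then asks when a fed baseline would change a table.

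**1. Time without food at the predose draw.**
- Fasting, as used in protocol 6.8.2 and 7.4.17: at least 8 h.
- Guaranteed at the 0-hour predose point (7.4.16): about 2 h.
- Possible shortfall: 8 − 2 = 6 h.

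**2. Can the predose sample still be fasted?** Section 7.4.17 says only that it is taken before MLN0128.
- *Meal before arrival.* A clinic draw that morning will not normally follow 8 hours without food.
- *Arrived fasted.* Arrival is about 3 h before the baseline ECG and breakfast ends at least 2 h before it. That leaves about 3 − 2 = 1 h, including the meal itself, for a fasted draw. No passage requires the draw in that interval.
- *Sample timed with the predose ECG.* Note e places the blood draw after the ECG, and so after the meal.
- *Earlier-day value under note a or k.* It could be fasted, but neither note requires it.

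Some baselines may be fed and some may be fasted. The documents do not give the split.

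**3. Effect on mean change.** Let f be the share of fed baselines and d the mean meal-related rise among them. Bias in the mean baseline = f × d, and mean change falls by the same amount if later values are fasted. Neither f nor d is in the documents. If either is zero, the bias is zero.

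**4. Effect on grade shifts.** Table 6-3 of the protocol puts Grade 1 at above ULN to 160 mg/dL. Take ULN = 110 mg/dL as an assumption (6.8.2 uses above ULN or ≥ 110 mg/dL as its trigger). Take true fasting baselines of 90, 100 and 110 mg/dL and later fasting values of 120 or 150 mg/dL, all assumed. Both later values are Grade 1. A 0→1 shift is still recorded only if true baseline + d ≤ 110.

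| Assumed d (mg/dL) | Recorded baselines | Baselines still showing 0→1 | Baselines now 1→1 |
|---|---|---|---|
| 0 | 90, 100, 110 | 90, 100, 110 | none |
| 10 | 100, 110, 120 | 90, 100 | 110 |
| 20 | 110, 120, 130 | 90 | 100, 110 |
| 40 | 130, 140, 150 | none | 90, 100, 110 |

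The values of d only show the mechanism; they do not estimate the rise after a light meal. A shift is lost only when the rise crosses a grade limit. Change from baseline moves by d in every case: for 100 to 120 mg/dL, a change of 20 becomes 0 at d = 20.

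**The case against.** **The fasting check in protocol 6.8.2.** When a site fasting-glucose reading is above ULN or ≥ 110 mg/dL, staff first confirm that the patient was fasting. Those are the readings that can alter a baseline grade. This stands as a partial safeguard. It serves clinical management, does not change which value SAP 5.4.2 selects, and does not reach lower readings that enter change from baseline.

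**The rise may be small.** Patients with diabetes are excluded, and the meal is light and ends at least 2 hours before the baseline ECG. This also stands; no size is claimed here.

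**Later values may not all be fasted.** SAP 5.10.2 puts unscheduled results in the shift tables. A non-fasted unscheduled value could raise the worst grade and offset the effect, so the net direction is not certain.

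**Pooling with panel glucose.** A reader might infer that the panel glucose of note k and the fasting glucose of note m are merged, with the last-evaluation rule deciding between them. The schedule has separate rows and nothing says they are pooled, so the point does not rely on it.

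**Importance.** The output is descriptive, in about 30 patients, with no hypothesis test, and the data stay in listings. That is a fair reason for low priority. It does not remove the contradiction over fasting state or supply the missing baseline condition.

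**Conclusion.** The point holds in a limited form. The protocol calls the Day -1 and Cycle 1, Day 1 glucose fasting while providing for a meal on both mornings, and the SAP baseline rule does not ask whether the value was fasted. Upward glucose shifts, and change from baseline if tabulated, may be understated. The size depends on the share of fed baselines and the meal-related rise, neither of which the documents give, and it may be zero.

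Three stronger readings are not supported:
- *All baselines are fed.* A draw before the site breakfast, or a recent earlier value under note a or k, may be fasted.
- *Shifts are understated.* That needs a rise large enough to cross a grade limit, as the table shows.
- *The main results are affected.* The QTc analyses do not use this baseline. The hyperglycemia adverse-event-of-interest table in SAP 5.10.1.1 is built from MedDRA preferred terms and does not use it either.

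The matter is confined to descriptive secondary safety output: a cheap improvement, minor priority.

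**What to change.** **SAP 5.4.2 and 5.10.2.**
1. Define the fasting-glucose baseline as the last predose value documented as fasted.
2. Keep values known to be non-fasted in the listings, but out of the fasting-glucose change and shift tables.
3. If no fasted Cycle 1, Day 1 or Day -1 value exists, use the screening fasting glucose, flag those patients, and show the shift table with and without them.

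**Protocol.** Reconcile section 4.1 with sections 7.4.16 and 7.4.17 and note m on the fasting state that applies at screening, Day -1 and Cycle 1, Day 1. Screening belongs in that list because inclusion criterion 7 relies on a fasting glucose although the stated fast begins only at Cycle 1, Day 4.

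**Data.** Record fasting status with each fasting-glucose sample, if the eCRF (not among the documents) does not already capture it.

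**Cost.** Two or three SAP sentences, four protocol passages to reconcile, and possibly one eCRF field. The screening fallback has its own drawbacks:
- The value may be up to 28 days old.
- Eligibility caps it at 120 mg/dL, so regression to the mean may inflate later upward shifts.
- It may predate the 7-day corticosteroid washout of exclusion criterion 7.

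These are the reasons for showing the table both ways. A few patients may have no qualifying baseline and would drop out of the fasting-glucose change and shift tables.

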#### **5.4.3 Windowing of Visits**

All data will be categorized based on the scheduled visit at which it was collected. These visit designators are predefined values that appear as part of the visit tab in the eCRF.

#### **5.4.4 Justification of Pooling**

All data from all sites will be pooled. Study center or treatment-by-center interaction will not be included in any statistical analysis.

#### **5.4.5 Withdrawals, Dropouts, Lost to Follow-up**

Patients who are withdrawn from treatment before completing study-required PK/ECG assessments for reasons other than DLTs will be replaced.

### **5.5 Patient Disposition**

Patient disposition will be summarized as the number and percentage of patients in the safety and PK populations, and the reason study drug was discontinued. All percentages will be based on the number of patients enrolled.

### **5.6 Demographics and Baseline Disease Characteristics**

#### **5.6.1 Demographics**

Demographic and baseline characteristics will be summarized. These include age, gender, ethnicity, race, height, weight and body mass index (BMI).

BMI = weight / height, where weight is in kilograms and height in meters.

#### **5.6.2 Medical History**

##### **5.6.2.1 General Medical History**

Medical history will be presented in by-patient listings.

### **5.6.2.2 Disease-Specific History**

The following disease-specific characteristics will be summarized: tumor type, stage, Eastern Cooperative Oncology Group (ECOG) performance status and site of cancer involvement. Percents are based on the number of patients in the safety population.

ECHO data collected at Baseline and Prior Therapies will be presented in by-patient listings.

## **5.7 Treatments and Medications**

### **5.7.1 Concomitant Medications**

Concomitant medications will be coded using the March 2014 version of the World Health Organization (WHO) Drug Dictionary Enhanced. The number and percentage of patients taking concomitant medications from the date of the first dose of study drug will be tabulated by generic term.

### **5.7.2 Study Treatments**

Patients will be required to swallow 8, 5-mg capsules for a total dose of 40 mg MLN0128 on Cycle 1, Day 1. To mitigate nausea and vomiting, patients will be administered an antiemetic agent on Cycle 1, Day 1 as an intravenous infusion (IV) over 30 seconds, at least 30 minutes before study drug administration. After completing the required PK/ECG assessments at Cycle 1, Day 3, patients may continue treatment with MLN0128. For patients continuing treatment with MLN0128, the drug is administered at a dose of 30 mg once weekly (QW) in continuous cycles of 28 days.

#### **5.7.2.1 Extent of Exposure**

The total amount of dose taken in mg, number of treated cycles and the relative dose intensity will be summarized in each cycle and overall. A treated cycle is defined as a cycle in which the patient received any amount of study drug. The numbers and percentages of patients who had 1, 2, 3 .....etc. treated cycles will also be presented.

Relative dose intensity (%) for MLN0128 is defined as  $100 \times (\text{total amount of dose taken} ((\text{mg})) / (\text{prescribed dose per day} * \text{total number of treated days in cycle} * \text{number of treated cycles}))$ .

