To mitigate nausea and vomiting known to occur at a 40 mg dose of MLN0128, patients will be administered an antiemetic agent (0.25 mg palonosetron) on Cycle 1, Day 1.

After collection of the 10-hour postdose PK/ECG assessment on Cycle 1, Day 1, patients will be furloughed from the study site. The Holter recorders will not be removed during this furlough

MLN0128**Clinical Study Protocol C31002 Protocol Amendment 2**

period.

On Cycle 1, Day 2 and Cycle 1, Day 3, patients may eat and drink up to approximately 2 hours before arriving at the study site for PK/ECG evaluations.

On Cycle 1, Day 2, patients will report to the clinical facility at least 1 hour before the 24-hour postdose PK/ECG (triplicate) assessments. After the PK/ECG assessments are completed, the Holter recorders will be removed and patients will be furloughed from the study site.

On Cycle 1, Day 3, patients will report to the clinical facility at least 1 hour before the 48-hour postdose assessments, which will represent the final study endpoint-specific planned PK/ECG assessments.

After completing the PK/ECG assessments on Cycle 1, Day 3, patients may continue to receive MLN0128 if, in the opinion of the investigator, the patient is deriving clinical benefit, until they experience disease progression. Patients continuing treatment with MLN0128 at the discretion of the investigator will receive a dose of MLN0128 up to 30 mg every week (QW). Dose escalation will not be permitted, and a maximum of 2 dose reductions (for patients experiencing study drug-related toxicity) will be permitted. Patients will return to the study site for follow-up visits at the time points in the [Schedule of Events](#). Treatment may continue until disease progression, unacceptable MLN0128-related toxicity, withdrawal of consent, or for up to 12 months (whichever occurs first). All patients enrolled in the study will attend the End of Study/Early Termination visit 30 (to 40) days after receiving their last dose of study drug.

Toxicity will be evaluated according to National Cancer Institute Common Terminology Criteria for Adverse Events (AEs), Version 4.03, effective date 14 June 2010. AEs will be assessed, and laboratory values, vital signs, and ECGs will be obtained to evaluate the safety and tolerability of MLN0128.

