After completing the required PK/ECG assessment period (Cycle 1, Day 3), patients may continue treatment with MLN0128 at the discretion of the investigator at a dose of MLN0128 30 mg QW. If patients experience severe emesis or mucositis preventing them from taking an MLN0128 dose, that dose will be skipped. If emesis occurs after study medication ingestion and whole capsule(s) are visible in the vomitus, replacement capsule(s) should be taken; otherwise the dose will not be re-administered, and patients should adhere to the dosing schedule and resume dosing at the next scheduled time with the prescribed dosage. Patients should record the time of the emesis in their dosing diary cards (see the Study Manual). Under no circumstance should a patient repeat a dose or double-up doses. Patients should be instructed to take their study medication at approximately the same time each week and not to take more than the prescribed dose at any time. Patients should swallow the study medication whole and not chew it, open it, or manipulate it in any way before swallowing. In the event, that, a patient fails to take the MLN0128 dose within the time frame specified (\pm 12 hours), that dose should be skipped. Patients should record any skipped doses in their dosing diary cards (see the Study Manual) and resume dosing at the next scheduled time with the prescribed dosage.

Starting at Cycle 1, Day 8, patients are advised to take their doses of study drug with a light meal.

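### The relative dose intensity formula applies one dose constant to a 40 mg first dose followed by a different weekly dose, so a fully compliant Cycle 1 cannot read 100%, and its undefined terms can hide skipped and reduced doses

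*SAP*

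**What the plan says.** SAP 5.7.2.1 (Extent of Exposure) puts total milligrams taken in the numerator and, in the denominator, "prescribed dose per day} * \text{total number of treated days in cycle} * \text{number of treated cycles". RDI is to be summarized for each cycle and overall. One of the terms is defined: "A treated cycle is defined as a cycle in which the patient received any amount of study drug". No definition is given for a treated day, or for which prescribed dose applies when the dose changes.

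SAP 5.7.2 (Study Treatments) describes two dose levels. For the first dose: "Patients will be required to swallow 8, 5-mg capsules for a total dose of 40 mg MLN0128 on Cycle 1, Day 1". For patients who continue: "the drug is administered at a dose of 30 mg once weekly (QW) in continuous cycles of 28 days".

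The protocol is less uniform on the continuation dose. Section 4.1 says patients "will receive a dose of MLN0128 up to 30 mg QW", and the Protocol Summary says the same. Footnote h to the Schedule of Events says they "will receive a maximum dose of 30 mg MLN0128 administered on a QW schedule". Section 6.1 has treatment continuing "at the discretion of the investigator at a dose of MLN0128 30 mg QW".

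Protocol 6.1 also requires some doses to be skipped (severe emesis or mucositis, or a missed ±12-hour window). Protocol 6.4 requires interruption for related toxicity of Grade 3 or higher and allows weekly doses of 20 mg and then 15 mg. SAP section 6 lists no change to the planned analyses, and neither document gives another denominator.

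**The concern.** The formula suits a drug given at one fixed dose on a fixed number of days per cycle. Here the first dose differs from every later one, dosing is weekly, and doses may be skipped or reduced. Four problems follow.

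1. **Cycle 1 and overall.** One constant cannot represent 40 mg once and then a lower weekly dose. Every treated patient has a Cycle 1.
2. **Overall value.** The formula multiplies one cycle's day count by the number of cycles. It has no defined value when cycles differ in dosing days.
3. **Skipped or held doses (depends on the reading).** If a treated day is a day on which drug was taken, parallel to the SAP's definition of a treated cycle, missed doses leave the denominator.
4. **Reductions (depends on the reading).** If the prescribed dose is the current reduced dose, a reduction does not lower RDI.

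Tolerability is part of the secondary objective, and RDI is one of the summaries that bear on it. As written, RDI can exceed 100%, can hide missed or reduced doses, and can differ between two programmers working from the same data.

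**Working it through.** The documents state no RDI value, so there is no figure to reproduce first.

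**Inputs.** First dose 40 mg (SAP 5.7.2). Later dose 30 mg weekly in 28-day cycles, so four weekly doses per cycle (SAP 5.7.2). Reduced levels 20 and 15 mg (Protocol 6.4). The 30 mg is used for illustration because the SAP states it.

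**Formula.** RDI = 100 × mg taken / (dose × days × cycles).

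**Compliant Cycle 1.** Taken = 40 + 3 × 30 = 130 mg.
- 30 mg × 4 days: 130/120 = 108.3%
- 40 mg × 4 days: 130/160 = 81.3%
- 28 calendar days: 130/(30 × 28) = 15.5%; 130/(40 × 28) = 11.6%
- Weekly dose divided by 7, × 28 days: again 108.3% or 81.3%

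Only a constant of 130/4 = 32.5 mg gives 100%, and no document prescribes it. The result does not depend on 30 mg. For a weekly dose w and four days, the ratio is (40 + 3w)/(4w) or (40 + 3w)/160, and each equals 1 only at w = 40.

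**Compliant course, overall, four days per cycle.**

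| Cycles | mg taken | 30 mg constant | 40 mg constant |
|---|---|---|---|
| 2 | 250 | 104.2% | 78.1% |
| 3 | 370 | 102.8% | 77.1% |
| 6 | 730 | 101.4% | 76.0% |
| 12 | 1450 | 100.7% | 75.5% |

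**Cycles of unequal length.** Suppose a patient takes 4, 3 and 2 doses in Cycles 1 to 3. Taken = 130 + 90 + 60 = 280 mg; planned = 40 + 11 × 30 = 370 mg, so 75.7% of plan. With the 30 mg constant and three cycles:
- day count 4: 280/360 = 77.8%
- day count 3: 280/270 = 103.7%
- day count 2: 280/180 = 155.6%

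If days are instead totalled over cycles and then multiplied by the number of cycles, cycles are counted twice: two compliant cycles read 250/(30 × 8 × 2) = 52.1%.

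**Skipped doses, if treated days means days dosed.** A later cycle with 2 of 4 doses reads 60/(30 × 2) = 100%, against 60/120 = 50% of plan. For a patient who continues treatment but misses Cycle 1 doses:

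| Cycle 1 doses | mg taken | 30 mg constant | 40 mg constant | Share of planned 130 mg |
|---|---|---|---|---|
| 3 | 100 | 111.1% | 83.3% | 76.9% |
| 2 | 70 | 116.7% | 87.5% | 53.8% |
| 1 | 40 | 133.3% | 100% | 30.8% |

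With either constant, RDI rises as doses are missed.

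**Reductions, if prescribed dose means the current dose.** Four doses of 20 mg read 80/(20 × 4) = 100%, against 80/(30 × 4) = 66.7% relative to 30 mg.

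**Where the formula works.** With 30 mg and four scheduled days, it is correct for each single cycle from Cycle 2 onward.

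**The case against.** RDI is not a study endpoint. Protocol 8.1.9 asks only that exposure be tabulated, the SAP has no decision rules, and the dose-limiting toxicity criterion of 75% of planned Cycle 1 doses does not use RDI. Total milligrams and number of treated cycles are reported alongside it, and SAP 5.7.2.2 summarizes action on study drug, so a short or reduced course stays visible. All of this stands and limits the consequence, but it does not make the RDI figure correct or reproducible.

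On the most natural reading (30 mg × 4 days), the error for a compliant patient is 8.3 points in Cycle 1 and falls to 0.7 points overall at 12 cycles. That also stands. The larger figures come from less natural readings, such as carrying 40 mg into later cycles or applying Cycle 3's day count to all cycles. They show how far the wording leaves the result open, not what a careful programmer would most likely report.

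The skipped-dose and reduction points are ambiguities rather than errors, and intake measured against the current prescribed dose is a coherent adherence measure. That is fair. The SAP must then state which measure it intends, since adherence to a reduced dose and intensity relative to plan answer different questions.

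Finally, the continuation-dose wordings may not contradict one another outright, because reductions below 30 mg are allowed. They still leave open whether a patient may start continuation below 30 mg, and so what the planned amount is.

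**Conclusion.** The concern holds. Under any single prescribed dose in the documents, a compliant four-dose Cycle 1 does not read 100%: it reads 108.3% or 81.3% with four dosing days and the SAP's 30 mg weekly dose. The overall value inherits this error and is undefined when cycles differ in dosing days. These two conclusions need no assumption about intent, only that the formula is applied as written.

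The loss of skipped doses from the denominator, and the invisibility of reductions, depend on how two undefined terms are read. The reach is limited to a descriptive exposure summary; the QTc analysis is unaffected. The point should be corrected before the exposure tables are programmed.

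**What to change.** Replace the formula in SAP 5.7.2.1 with RDI = 100 × total mg taken / total mg planned, by cycle and overall. Define planned mg as a sum over scheduled dosing dates while on treatment:

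- the 40 mg Cycle 1, Day 1 dose; and
- for patients who continue, the weekly dose originally assigned at continuation, for each scheduled date, with skipped, held and reduced doses counted at that assigned amount.

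Patients who stop after the single dose have 40 mg planned. State when the on-treatment period ends, so that a partial final cycle is handled the same way for everyone. If adherence to the current dose is also of interest, report it separately under its own name.

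With the SAP's 30 mg, a compliant Cycle 1 becomes 130/130 = 100%, a later cycle with 2 of 4 doses becomes 50%, and the 4/3/2-dose course becomes 75.7%.

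The continuation-dose wordings in the Protocol Summary, Protocol 4.1, Schedule of Events footnote h, Protocol 6.1 and SAP 5.7.2 must be reconciled so that the planned amount is unambiguous.

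The cost is one SAP definition and its programming. No new data are needed if the weekly dose assigned at continuation is recorded. Reported dose intensity may look less favourable.
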